7. SUMMARY OF BASELINE INFORMATION

7.1 Patient Enrollment and Accountability

The following will be tabulated via frequency and percentage into a summary table:

- Number of included and randomized patients
- Number of randomized patients by treatment groups
- Number of active sites
- Number of included and randomized patients by treatment groups
- Number of included and randomized patients by site
- Number and percentage of patients having finished the study normally by treatment groups
- Reason of withdrawal will also be tabulated and a listing of reason of withdrawal will be produced
- Normal study end (yes/no) and if no, reason

Moreover, subjects who withdraw from the study will be tabulated with the reasons for the withdrawal. Compliance with study visits will also be presented. Please refer to section 4 for enrolled subject definition. Also, please see the protocol for the enrollment diagram and enrollment timeline diagram.

7.2 Demographics and Baseline Characteristics

The baseline characteristics and demographics of each study subject will be collected during the subject screening process. For subject demographics, age, sex, race, ethnicity, and other demographic variables will be used for each summary. All outcomes will be presented using descriptive statistics; normally distributed data by the mean and standard deviation (SD) and skewed distributions by the median and interquartile range (IQR). The sample size of non-missing values will be reported for summary tables as well as frequency (count and percentage) of illegible and eligible will be represent by a Consolidated Standards of Reporting Trials (CONSORT) consort diagram. The number and reasons for drop-out, lost-to-follow-up, or withdrawal will be presented by frequency and percentage.

7.3 Medical History and Prior Intervention

The subject's medical historical data will be recorded on an electronic case report form (eCRF). Historical data will be summarized into tables with continuous variables being represented by medians and interquartile ranges and categorical

 Edwards	Revision Date: May 11, 2022	Rev	A	For Use Only by Affiliates of Edwards Lifesciences	Page 12 of 19
	Title	Statistical Analysis Plan for HPI SMART-BP Trial			

variables being represented by counts and percentages.

7.4 Baseline Risk Assessments

Demographic data will be summarized into tables with continuous variables represented by median and interquartile ranges. Categorical demographic variables will be represented by counts and percentages

The vascular access obtained is standard clinical care for the adult population and the addition of the Acumen IQ sensor or FloTrac sensor is not expected to impose any additional risk to the patient. There is no measurable increased infectious risk with the temporary use of the Acumen IQ sensor or FloTrac sensor. Below is a list of anticipated risks that may be associated with the use of the ForeSight Oximetry Sensors:

- Allergic reaction to adhesive on sensors
- Skin irritation

7.5 Procedural Information

Procedural data (procedure setting and procedure measurements) will be summarized into tables with continuous variables being represented by medians and interquartile ranges and categorical variables being represented by counts and percentages. Moreover, a specifications document is created for each statistical output (table, listing, or figure) and it will contain, at the minimum:

- Title and footnote information
- Column headers
- If the output includes a figure then a detailed description of the figure
- Variables, procedures, and/or calculation logic used in the statistical output
- Ad Hoc or Post Hoc analyses
- Formulas for derived procedures

8. STATISTICAL ANALYSIS OF STUDY ENDPOINTS

8.1 Primary Effectiveness Endpoint

The primary objective is to determine if the use of a protocolized strategy using advanced hemodynamic monitoring with Hypotension Prediction Index (HPI) software guidance for intraoperative hemodynamic management reduces postoperative complication rate in moderate- to high-risk non-cardiac surgery patient. The treatment group (Acumen ID sensor) will be compared to control arm receiving standard of care (FloTrac sensor). This analysis will be conducted on the mITT population only with pivotal study subject. With null hypothesis, the Z-statistic will be used to judge if the hypotension prediction index software can reduce postoperative morbidity and mortality:

$$Z = \frac{\hat{p}_0 - \hat{p}_1}{\sqrt{\frac{\hat{p}_0(1-\hat{p}_0)}{n_0} + \frac{\hat{p}_1(1-\hat{p}_1)}{n_1}}}$$

Here x_0 and x_1 are composite endpoint events in the reference arm and treatment arm respectively; thus, $\hat{p}_0 = \frac{x_0}{n_0}$, $\hat{p}_1 = \frac{x_1}{n_1}$ are the proportion of events in the reference arm and treatment arm, respectively; n_0 , n_1 are the number of subjects in

 Edwards	Revision Date: May 11, 2022	Rev	A	For Use Only by Affiliates of Edwards Lifesciences	Page 13 of 19
	Title	Statistical Analysis Plan for HPI SMART-BP Trial			

reference arm and treatment arm respectively; $\frac{\hat{p}_0*(1-\hat{p}_0)}{n_0}$, $\frac{\hat{p}_1*(1-\hat{p}_1)}{n_1}$ is the variances of the proportion of events in reference arm (\hat{p}_0), and in test arm (\hat{p}_1) respectively. The Z-statistic will compare to the critical Z-value to judge if the null hypothesis could be rejected.

By the study designed parameter table in section 2.3 and the Z statistic calculated at each study stage with the trial data collected at present stage in addition to data collected in previous stage or stages, following judgement will be conducted for interim analysis and final analysis. For first and second interim analyses, if the calculated Z value is equal to or less than the critical Z value in the effectiveness boundary column, the null hypothesis will be rejected, and the study will stop for achieving the study objective; if the calculated Z statistic is greater than critical Z value for effectiveness but it is close to the critical value but could not reject null hypothesis, the study continues to next step, and the study sample seize will be reassessed by the principles of adapted group sequential study design. If it is necessary, more study subject will be enrolled for the purpose to achieve the study objectives. For final analysis, if the calculated Z statistic is equal to or less than the critical Z value listed in effectiveness boundary column, the null hypothesis will be rejected, and the alternative hypothesis will accept, the study objective is achieved, otherwise, the null hypothesis will accept, the study objective will be not achieved.

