- Monitoring Phase: HPI 50 – 85 → evaluate flow / vascular tone indices and fluid responsive state.

Figure 1 : Treatment Protocol for Subjects Enrolled in the Treatment Arm

HPI Pressure & Flow Optimization Protocol

Note: Clinicians should validate the appropriateness of protocol recommendations, and provide treatment based upon their clinical judgment.

THIS DOCUMENT CONTAINS CONFIDENTIAL AND PROPRIETARY INFORMATION OF EDWARDS LIFESCIENCES, LLC. IT MAY NOT BE REPRODUCED OR DISCLOSED WITHOUT PRIOR WRITTEN PERMISSION FROM EDWARDS LIFESCIENCES, LLC.

Edwards Lifesciences, Edwards, the stylized E logo, HemoSphere, Acumen, Acumen IQ, FloTrac, and ForeSight Elite oximetry Sensor are trademarks of Edwards Lifesciences Corporation.

Randomization and Blinding

The randomization for this Trial will be implemented using an Interactive Web Response Systems (IWRS). The Sponsor will be blinded to the randomization codes. Participants will be randomized to either the control or treatment arm at enrollment. Study investigators will be blinded up until the time of the surgery. The clinician(s) involved in the consenting of the patient will be blinded to the randomization assignment and will not be involved in the care of the Trial subject. Once the intent of arterial line placement is confirmed with the anesthesia team, before surgery (the day before or in the morning of surgery), the subject will be randomized to either the treatment or control arm. The arterial line will then be placed. Randomization will be allocated in 1:1 ratio, stratified by site.

[figure not shown]

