2.4 Randomization and Blinding

The enrolled subjects will be randomized to treatment arm and control arm with 1:1 ratio. To avoid the selection bias caused by study team, the randomization will be done automatically by the Electronic Data Capture (EDC) system.

Randomization will occur after verifying an arterial line that is placed during the study procedure. A block randomization scheme with alternating block sizes of 4 and 6 subjects will be generated by study subject enrolled at each study site. No other stratification factors will be considered in randomization. By the random number generated for each subject within the randomization block, the web-based program will produce a cutoff value to ensure equal allocation between the treatment and control arms. The randomization code for each subject will be maintained by the study coordinator at the study site. The treatment allocation will be unblinded once the surgery operation starts.

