3.2 Exploratory Analysis Datapoints

The following measures will also be investigated for this study:

1. Time-to-Adverse Event (Complications) Analysis
 - a. Non-Parametric Survival Analysis (KM approach)
 - b. Cox Proportional Hazard Model
 - c. Mixed effect Cox Proportional Hazard Model
 - d. Stratification analysis through applying study sites, gender, race as the stratification factor
 - e. Fixed/Mixed effective Poisson regression model applying the count of events as the response
 - f. Mixed effective survival model to assess the multiple event cases within patient

 Edwards	Revision Date: May 11, 2022	Rev	A	For Use Only by Affiliates of Edwards Lifesciences	Page 8 of 19
	Title	Statistical Analysis Plan for HPI SMART-BP Trial			

2. Hypotension management analysis
 - a. Time from alert event to intervention
 - b. % alerts with no intervention
 - c. Reasons for nonintervention
 - d. Amount of hypotension removing nonintervention segments
 - e. Agreement analysis; clinical decision vs. treatment algorithm
 - f. Overall treatment protocol compliance
3. Hypotension duration (minute) is the summation of hypotension instance duration, defined as the consecutive measurements with MAP<65 lasting at least 1 minute.
4. Area under the curve (AUC) with the MAP threshold of 55,65,75 mmHg
5. Time Weighted Average (TWA) of intraoperative hypotension (mmHg)
6. Time in target SVV <13% (for valid SVV readings = no arrhythmia)
7. Time in target CI >2.5 L/min/m15
8. Postoperative morbidity survey (POMS) on postoperative day 3
9. Transfusion requirement (mL packed red blood cells)
10. Amounts of intraoperative crystalloid and colloid and vasoactive drugs; mL
11. Amount of vasoactive drugs; mg (e.g.: phenylephrine, ephedrine, norepinephrine, epinephrine, dobutamine)
12. Amount of intraoperative intravenous analgesics and sedatives
13. Brain oxygen saturation – StO2 using ForeSight Elite tissue oximetry system, time in target
14. Verification of the incidence of the listed postoperative complications may be performed at each site by reviewing historic data up to 6 months prior to study initiation
15. Cost of care
16. Hospital length of stay
17. Hospital readmission within 30 days

Please see appendix section 12.9 for TWA calculation.

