6. DATA AND ANALYSIS CONVENTIONS

6.1 General Conventions

The baseline characteristics and demographics, the medical history data of each study subject will be collected during the subject screening process and recorded on an electronic case report form (eCRF). The hemodynamic measurement data will be downloaded from HemoSphere advanced monitoring platform.

All endpoints will be presented using descriptive statistics by assigned treatment group; continuous variable will be summarized with the mean, standard deviation (SD), median, and interquartile range (IQR); binary and categorical variables will be presented using count and percentage.

Other summaries (e.g., minimum, maximum, standard error, 95% intervals, coefficient of variation (CV) or %CV, odd ratio) will be used as appropriate. Sample sizes shown with summary statistics are the number (n) of patients with non-missing values. All percentages should be rounded and reported to a single decimal place (xx.x%). If percentages are reported as integers, percentages greater than 0% but <1% will be reported as <1%, whereas percentages greater than 99% but <100% will be reported as >99%. A percentage of 100% will be reported as 100%.

For categorical endpoints, logistic regression and the approximate Z test will be performed on the primary outcomes and exploratory analysis. Summary statistics and p-values from the statistical comparison will be displayed in result report. The p-value will present with three decimals. P-values less than 0.001 will be reported as <0.001. Additionally, ad-hoc analyses may be conducted as deemed appropriate.

An independent Data Safety Monitoring Board (DSMB) will evaluate the data at interim.

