8.4 Sensitivity Analysis

Sensitivity analysis will be performed for primary endpoint. For primary effective endpoint, sensitivity analysis will be conducted with all study subjects from FAS, PP, or CC population to check if the similar conclusion could be drawn. If there are more than 5% study subjects with missing primary endpoint in test arm, the imputed endpoint with missing at complete random, or missing not at random will replace the missing value for each study subject, the sensitivity analysis on this imputed mITT pivotal dataset will be conducted to check if the similar conclusion could be drawn. Then check if the variation among study sites will affect the statistical comparison between study arms. Next check if the study cohorts (roll-

 Edwards	Revision Date: May 11, 2022		Rev	A	For Use Only by Affiliates of Edwards Lifesciences	Page 14 of 19
	Title	Statistical Analysis Plan for HPI SMART-BP Trial				

in, pivotal) will change the analytical conclusion. Finally, bootstrap approach will be applied to check if sample size effect the analytical result.

The effect of the following factors on the primary effectiveness endpoint will be analyzed:

- MAP threshold (<55, 60, 70 mmHg) and the length of time in hypotension episode definition (20, 40, and 80 seconds)
- NSQIP score vs ASA score
- Regional anesthesia vs general anesthesia
- Surgery technique (open or laparoscopic) vs hemodynamic changes
- Patient positioning vs hemodynamic changes
- Surgery type vs hemodynamic changes
- Survival analysis
- Arterial line vs Arterial line + CVP monitoring
- Onset of HPI Alert vs time of intervention
- Amount of vasopressors/fluids/inotropes administered vs time of intervention (start & stop time)
 - Stratified by cohort
- Tidal volume

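### Randomisation is blocked within site, but the Z statistic that decides every look ignores site; the test stays valid but forgoes about 0.2 to 2 points of power under assumed between-site SDs of 5 to 15 points

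*Combined protocol and SAP*

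**What the plan says.** **Allocation.** Protocol section 4 (Randomization and Blinding) states: "Randomization will be allocated in 1:1 ratio, stratified by site". SAP 2.4 gives the mechanism: "A block randomization scheme with alternating block sizes of 4 and 6 subjects will be generated by study subject enrolled at each study site". It adds: "No other stratification factors will be considered in randomization".

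**Decision rule.** SAP 8.1 introduces the primary test with "With null hypothesis, the Z-statistic will be used to judge if the hypotension prediction index software can reduce postoperative morbidity and mortality". The statistic is the difference of the two crude proportions divided by √(p0q0/n0 + p1q1/n1). The same section applies "the Z statistic calculated at each study stage with the trial data collected at present stage", together with the data from earlier stages, to the boundary at both interims and the final. Protocol section 7 (Analysis Methods) gives a pooled-variance version, also without a site term.

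**Where site does appear.** SAP 8.4 lists an unspecified check: "Then check if the variation among study sites will affect the statistical comparison between study arms". SAP 3.2 has, under the exploratory time-to-event analyses, "Stratification analysis through applying study sites, gender, race as the stratification factor". SAP 6.1 says "For categorical endpoints, logistic regression and the approximate Z test will be performed on the primary outcomes and exploratory analysis", but names no covariates and gives the logistic model no part in the decision. None of these can alter whether a boundary is crossed.

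**The concern.** Blocking within site forces the arms to be nearly equal at every site. Differences in event rate between sites therefore contribute almost nothing to the sampling error of the treatment difference. The variance in SAP 8.1 is the one for simple randomisation and still includes them. When site rates differ, the denominator of Z is too large, Z is pulled towards zero, and the real type I error falls below the level the boundaries were built for.

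Some heterogeneity between sites is likely. The trial mixes several surgical specialties at up to 20 sites, and the myocardial injury threshold depends on the troponin assay. The same Z also governs early stopping, and under SAP 8.1 a value near the boundary prompts reassessment of the sample size. What is at stake is precision the design has already bought but the analysis does not use.

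**Working it through.** **Inputs.**
- Control rate 0.31 and a 25% relative reduction (SAP 2.3), so 0.2325 on treatment.
- Boundaries 2.96259, 2.35898 and 2.01404 in absolute value at 50, 75 and 100% information (SAP 2.3). Overall one-sided alpha 0.025.
- Up to 20 sites (protocol synopsis).
- 1,426 pivotal subjects (protocol section 7). Taking off the 15% attrition in SAP 2.3 gives (1,486 − 60) × 0.85 = 1,212 evaluable.
- Between-site SD of the control rate: not in the documents. **Assumed**, with a range of 0 to 15 points.

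**The plan's own figures.** The boundaries reproduce: simulated over three looks, overall one-sided alpha is 0.0249. The sample size does not. With these boundaries 80% power needs about 1,044 subjects (efficacy bounds only) or 1,095 (with the protocol's futility bounds), or about 1,228 and 1,288 after dividing by 0.85. That is a separate matter and does not affect the direction of this point. Power at 1,212 is about 0.855, and at 1,426 about 0.91.

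**Size of the excess variance.** Per subject, SAP 8.1 uses V = p0q0 + p1q1 = 0.31 × 0.69 + 0.2325 × 0.7675 = 0.2139 + 0.1784 = 0.3923. With blocking in site, the true value is V − s0² − s1², where s0 and s1 are the between-site SDs in the two arms. With a constant relative risk, s1 = 0.75 s0, so s0² + s1² = 1.5625 s0².

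| s0 | 1.5625 s0² | (true / planned variance) | true / planned SE |
|---|---|---|---|
| 0.05 | 0.0039 | 0.990 | 0.995 |
| 0.10 | 0.0156 | 0.960 | 0.980 |
| 0.15 | 0.0352 | 0.910 | 0.954 |

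If site effects are instead normal on the logit scale, s1 is a little larger and the planned variance is 1.1%, 4.6% and 11% too large. That is the information from about 13, 53 and 121 of 1,212 subjects.

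**Effect on the first interim, by hand.** At 1,212 the planned SE is √(0.3923/606) = 0.02544, so the expected final Z is 0.0775/0.02544 = 3.046, and 3.046 × √0.5 = 2.154 at the first look. For SD 15 with constant relative risk:
- Crude Z: mean 2.154, SD 0.954. P(Z ≥ 2.96259) = 1 − Φ(0.809/0.954) = 0.198.
- Stratified Z: mean 2.154/0.954 = 2.257, SD 1. P(Z ≥ 2.96259) = 1 − Φ(0.705) = 0.240.

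**Simulation.** The trial was simulated with 20 equal sites, blocks of 4 and 6 within site, 1,212 subjects, logit-normal site effects and efficacy boundaries only. The crude unpooled Z was compared with a Mantel-Haenszel risk difference and Sato variance on the same data (40,000 trials per power figure, Monte Carlo SE 0.0018; 120,000 per type I figure, SE 0.0005).

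| SD (points) | Overall power, crude / stratified | Stop at look 1 | Stop by look 2 | One-sided type I error |
|---|---|---|---|---|
| 0 | 0.854 / 0.854 | – | – | 0.0256 (crude) |
| 3 | 0.855 / 0.856 | – | – | – |
| 5 | 0.857 / 0.860 | 0.208 / 0.210 | 0.618 / 0.622 | 0.0254 / 0.0260 |
| 10 | 0.859 / 0.870 | 0.205 / 0.222 | 0.616 / 0.635 | 0.0216 / 0.0244 |
| 15 | 0.868 / 0.890 | 0.200 / 0.244 | 0.622 / 0.666 | 0.0190 / 0.0250 |

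**Robustness.**
- Group-sequential calculation with constant relative risk at 1,212: differences of 0.23, 0.93 and 2.04 points for SDs of 5, 10 and 15.
- Beta-distributed site rates: 0.13, 0.78 and 1.86 points.
- Unequal sites, one at the 20% cap and the smallest with 8 subjects: power 0.858 vs 0.860, 0.860 vs 0.870 and 0.862 vs 0.882.
- Small-site pooling rule applied, unequal sites opening at different times: gains of 0.2, 1.0 and 2.1 points, with stratified type I error near 0.025.
- All 1,426 subjects: 0.1, 0.6 and 1.5 points.

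**The case against.** The case for leaving SAP 8.1 alone is reasonable. The crude test is valid, slightly conservative and above its planned power whatever the site SD; in the table its power even rises with the SD. So nothing is lost against the plan, and what is described is a gain from a different valid method. The size rests on SDs the documents do not give, and the top case is wide: at 15 points, 95% of sites would have control rates between about 8% and 65%. At 5 points the gain is only 0.2 to 0.3 points. If almost all of the 1,426 contribute data, as the SAP's expectation of under 1% missing endpoints suggests, the gain is smaller throughout. The calculations leave out sample-size reassessment. The event-count limits in SAP 2.3, meant to keep the interim decision simple, would no longer work.

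Most of this stands as a description of scale. It is also true that the interim looks gain more than the final power only at SDs of 10 and 15; at 5 points the differences are similar and negligible. It does not remove the point. The stratified test holds the level the boundaries assume, costs essentially nothing when sites are alike, and needs no further data. The count table is a convenience that follows from the Z rule, not a reason to choose it.

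**Conclusion.** The point holds as a modest efficiency improvement that should be made. The primary analysis does not match the randomisation, and site-related analyses elsewhere in the SAP have no bearing on the decision. Relative to a site-stratified Z, the crude Z gives up about 0.2 to 2 points of overall power, and up to about 4 points in the chance of stopping at the first interim, for assumed between-site SDs of 5 to 15 points. These figures assume 1,212 evaluable subjects, 20 sites, the planned effect and efficacy boundaries only. Type I error of the crude test falls to about 0.019 at the top of that range. The direction is certain whenever site rates differ; the magnitude depends on an SD that only the trial data can supply.

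**What to change.** Before any unblinded look, replace the statistic in SAP 8.1 with wording such as:

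> Z = RD / SE(RD), where RD is the Mantel-Haenszel risk difference (treatment minus control) over sites with weights n1k·n0k/nk, and SE is its stratified (Sato) standard error. Sites with fewer than 10 subjects, or with an empty arm at a look, form one stratum.

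Report RD with its confidence interval and keep the crude Z as a sensitivity analysis. This Z is negative when treatment is better, which suits the negative boundaries in SAP 2.3; the printed formula is control minus treatment and has the opposite sign.

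The cost is low but not nil:
- A pooling rule has to be fixed in advance; the threshold of 10 is an example.
- The event-count limits in SAP 2.3 (111/74, 167/131, 222/186) cannot be read against a stratified Z, and should be dropped or marked as illustrative.
- The pooled Z and its interval in protocol section 7 must be brought into line.

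Adjusting for the NSQIP score is optional. It is not a stratification factor, so leaving it out does not bias the standard error. Including it would need a rule for missing scores, because footnote 5 of the Schedule of Events makes its collection conditional on availability. If the sponsor prefers the crude Z, the SAP should at least say that it is a deliberate conservative choice.

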Assuming a power of 80% and a relative reduction of at least 25% in the composite score (reference proportion=0.31) with three total looks (two interim analysis, one final), the critical values for each time point were chosen to preserve an overall type-1 error rate of 0.05. The O'Brien and Fleming methodology was used to determine the boundary rule for deciding when to stop the trial prematurely. Futility was included. A relative reduction in the composite outcome within the treatment arm is expected. The alpha at each interim and the maximum number of observations are chosen so that the overall significance level is the probability of detecting the treatment difference under the null hypothesis. The table below shows the critical values:

Analysis	Information Rate	Effectiveness Boundary z-value (Upper, Lower)	Futility Boundary z-value (Upper, Lower)
First Interim Analysis	50%	(2.96259, -2.96259)	(0.40273, -0.40273)
Second Interim	75%	(2.35898, -2.35898)	(1.12741, -1.12741)
Final Analysis	100%	(2.01404, -2.01404)	(2.01404, -2.01404)

THIS DOCUMENT CONTAINS CONFIDENTIAL AND PROPRIETARY INFORMATION OF EDWARDS LIFESCIENCES, LLC. IT MAY NOT BE REPRODUCED OR DISCLOSED WITHOUT PRIOR WRITTEN PERMISSION FROM EDWARDS LIFESCIENCES, LLC.

Edwards Lifesciences, Edwards, the stylized E logo, HemoSphere, Acumen, Acumen IQ, FloTrac, and ForeSight Elite oximetry Sensor are trademarks of Edwards Lifesciences Corporation.

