 Edwards	Revision Date: May 11, 2022		Rev	A	For Use Only by Affiliates of Edwards Lifesciences	Page 6 of 19
	Title	Statistical Analysis Plan for HP/ SMART-BP Trial				

estimation, and is supported by the integrated evidence from physician clinical experience, scientific publications, and previous clinical trial results.

The hypothesis setting for this study used in sample size estimation is:

$H_0: P_1 \geq P_0$

$H_1: P_1 < P_0$

where p_1 and p_0 are the proportions of composite endpoint in treatment arm and control arm, respectively.

Moreover, two interim analyses will be designed at 50% and 75% subject enrollment with 30-day follow-up data, to assess the composite endpoint (pooled event rate) between treatment and control arms. To determine when the trial can be stopped prematurely for effectiveness, the O'Brien-Fleming methodology¹⁶ was used to determine the stopping boundary (alpha spending function). The O'Brien-Fleming methodology preserves the overall type I error across all interim analyses¹⁶. The overall type I error used for this one tail hypothesis test study is 0.025. If the Z-statistics is close to boundary value but could not reject null hypothesis, possibly the study sample size will be reassessed for the purpose to achieve study objective.

With these trial parameter and hypothesis settings, and two designed interim analyses plus a final analysis, 1486 subjects (including 15% attrition, including a maximum of 60 roll-ins) are needed for this clinical trial. The sample size is estimated with PASS2021. The critical Z value and the corresponding p value for effectiveness boundary are displayed in the following table for interim analysis and final analysis. By the study objective and experiment design, in effectiveness analysis if the Z value calculated by the data available at each study stage (interim analysis and final analysis) is less or equal the critical Z value listed in effectiveness boundary column, the null hypothesis will be rejected, and the study stops for the study objective is achieved. To simplify the interim analysis decision making procedure, the lower limit of the reference arm accumulated subjects with complication, and the upper limit of treatment arm accumulated subjects with complication are designed by the study design parameters, the study arm accumulated sample size at each analysis stage, and effectiveness boundary (critical Z value) estimated by O'Brien-Fleming methodology.

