Analysis	Information Rate	Alpha Spending Function	Effectiveness Boundary Critical Z value	P-Value
First Interim	50%	O'Brien-Fleming	-2.96259	0.00153
Second Interim	75%	O'Brien-Fleming	-2.35898	0.00916
Final Analysis	100%	O'Brien-Fleming	-2.01404	0.02200

Analysis	Information Rate	Proportion of Control Subject with Complications	Required Reduction Rate	Control Arm Limit (2::)	Treatment Arm Limit (<)	Subject Ratio(<)*
First Interim	50%	0.31	0.33	111	74	0.67
Second Interim	75%	0.31	0.21	167	131	0.78
Final Analysis	100%	0.31	0.16	222	186	0.84

Note: * Subject Ratio = Treatment Arm Limit / Control Arm Limit.

 Edwards	Revision Date: May 11, 2022		Rev	A	For Use Only by Affiliates of Edwards Lifesciences	Page 7 of 19
	Title	Statistical Analysis Plan for HPI SMART-BP Trial				

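### SAP 8.1 computes Z as control minus treatment but declares success at negative boundaries, so the primary test as printed can reject only towards harm

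*Combined protocol and SAP*

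**What the plan says.** **Statistic.** SAP 8.1 prints Z = (p0-hat − p1-hat)/SE with an unpooled standard error. It states that p0-hat and p1-hat "are the proportion of events in the reference arm and treatment arm, respectively". An event is a patient with the composite complication.

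**Rule.** The boundary table in SAP 2.3 lists only negative effectiveness values: -2.96259, -2.35898 and -2.01404 at 50%, 75% and 100% information. SAP 2.3 says that if Z "is less or equal the critical Z value listed in effectiveness boundary column, the null hypothesis will be rejected". SAP 8.1 repeats this for the interims ("if the calculated Z value is equal to or less than the critical Z value in the effectiveness boundary column, the null hypothesis" is rejected) and for the last look: "For final analysis, if the calculated Z statistic is equal to or less than the critical Z value listed in effectiveness boundary column", the objective is met.

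**Re-estimation trigger.** SAP 8.1 reassesses the sample size when Z "is greater than critical Z value for effectiveness but it is close to the critical value".

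**Direction of benefit.** SAP 2.3 sets H0: P1 ≥ P0 against H1: P1 < P0, one-tailed at 0.025. It also gives, as a decision aid, "the lower limit of the reference arm accumulated subjects with complication, and the upper limit of treatment arm accumulated subjects with complication": control at least 111/167/222 and treatment below 74/131/186.

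**Protocol.** Section 7 prints symmetric boundaries, for example "2.96259, -2.96259", with overall type I error 0.05. It states a two-sided comparison with H0: p0 − p1 ≥ 0 and H1: p0 ≠ p1.

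**The concern.** The formula and the rejection rule point in opposite directions. Under the SAP 8.1 formula a benefit moves Z upwards, but the rule looks for Z far below zero. A program written faithfully from SAP 8.1 would miss a real reduction in complications and would report the objective as achieved when treatment did harm.

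The same sign runs through the re-estimation trigger. A promising first-interim result of Z = +2.5 lies 2.5 − (−2.96259) = 5.46 above the critical value, so it could not count as close to it.

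For any result strong enough to cross, the Z rule and the count table disagree. If that is first noticed at an interim, the sign of the primary test has to be settled after unblinded results exist.

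**Working it through.** **Inputs.** Boundaries, hypotheses and count limits: SAP 2.3. Z formula: SAP 8.1. Control rate 0.31 and 25% relative reduction, so p1 = 0.31 × 0.75 = 0.2325: SAP 2.3. N = 1426, so 713 per arm: protocol section 7. Assumptions: 606 per arm as a lower case (1426 × 0.85 / 2, using the SAP's 15% attrition), and an illustrative harm rate of 0.31 × 1.25 = 0.3875.

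**1. The plan's own p-values.** Lower-tail normal probabilities are Φ(−2.96259) = 0.00153, Φ(−2.35898) = 0.00916 and Φ(−2.01404) = 0.02200. All three match the SAP table. The minus signs are therefore deliberate, and the boundaries suit a statistic oriented treatment minus control.

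**2. The SAP's count limits in the SAP's formula,** with Z = (p0-hat − p1-hat)/√[p0-hat(1−p0-hat)/n + p1-hat(1−p1-hat)/n]:

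| Look | n per arm | Control | Treatment | Difference | SE | Z | Printed rule | Met? |
|---|---|---|---|---|---|---|---|---|
| 50% | 356.5 | 111 (0.3114) | 74 (0.2076) | 0.1038 | 0.0326 | +3.18 | ≤ −2.96259 | No |
| 75% | 534.75 | 167 (0.3123) | 131 (0.2450) | 0.0673 | 0.0273 | +2.46 | ≤ −2.35898 | No |
| 100% | 713 | 222 (0.3114) | 186 (0.2609) | 0.0505 | 0.0239 | +2.11 | ≤ −2.01404 | No |

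Fewer treatment events than these only push Z further up. Swapping the arms, so that treatment has the excess, gives −3.18, −2.46 and −2.11, and the printed rule then declares success at every look. With 606 per arm the values are +3.29, +2.55 and +2.19; a pooled SE does not change the direction.

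**3. Operating characteristics.** The expected final Z is (p0 − p1)/SE. At 713 per arm, under the planned effect, this is 0.0775/0.02346 = +3.30; under the illustrative harm it is −0.0775/0.02516 = −3.08. At 606 per arm the values are +3.05 and −2.84. Numerical integration over the three looks, effectiveness boundaries only, gives:

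| Probability of declaring success | 713 per arm | 606 per arm |
|---|---|---|
| Literal rule, planned benefit (0.31 vs 0.2325) | about 2e-7 | about 6e-7 |
| Literal rule, no difference | 0.025 | 0.025 |
| Literal rule, illustrative harm (0.31 vs 0.3875) | 0.86 | 0.80 |
| Sign corrected, planned benefit | 0.91 | 0.85 |

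The first entry can be bounded by hand. The chance of crossing at each look, Φ(boundary − 3.304√t), is 5.8e-8, 8.9e-8 and 5.2e-8 at t = 0.5, 0.75 and 1, which sum to 2.0e-7.

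**The case against.** The strongest reply is that nobody would be misled. The objective, H1, the lower-tail p-values and the count table all point to a reduction. SAP 2.3 is coherent alone, so the fault is one transposed numerator in SAP 8.1. On this view the 2e-7 and 0.86 describe a misprint applied blindly, and the 0.86 also needs an assumed harm rate. It is fair that the intent can be recovered and that these figures describe the literal text, not a likely outcome. But the statistic and its rejection rule are what a SAP must fix in advance, and the re-estimation trigger carries no directional cue of its own.

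A second reply is that a two-sided reading rescues the rule. SAP 2.2 describes stopping when |Z_i| ≥ c_i, and the protocol's boundaries are symmetric, so a positive Z would cross. The SAP 2.2 sentence is a generic description of the method, whereas SAP 2.3 and 8.1 state the operative rule. A two-sided reading also conflicts with the one-tailed 0.025 test, and would let harm reject H0 and count as success.

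The protocol cannot settle the direction: its null contains benefit and overlaps its alternative, and the subscripts of its own Z formula are not legible in the text available.

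Two smaller points stand. The count limits are slightly stricter than the boundaries: at the stated control counts, treatment counts up to 76, 132 and 187 still cross, against printed limits of 74, 131 and 186. That narrow gap is a separate matter. If the protocol's futility bounds are applied as binding, corrected power is about 0.89 and 0.84 instead of 0.91 and 0.85.

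**Conclusion.** The concern holds and should be fixed before any unblinded look. As printed, the SAP's primary decision rule rejects only when treatment has more complications than control, contrary to its own H1 and count table. The contradiction is one of sign and depends on neither the sample size nor the choice of standard error. Its size at 713 per arm is a success probability of about 2e-7 instead of 0.91 under the planned effect; the 606-per-arm case gives the same picture. Once the sign is corrected, the boundaries deliver the intended one-sided 0.025.

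The protocol's misdirected null, and its two-sided 0.05 against the SAP's one-sided 0.025, are related but separate defects.

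**What to change.** **SAP, preferred.** In 8.1 print Z = (p1-hat − p0-hat)/SE and keep the negative boundaries and the existing inequality. This single edit also repairs the re-estimation trigger. The count limits then give −3.18, −2.46 and −2.11, and all three cross.

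**SAP, alternative.** Keep control minus treatment and reject when Z ≥ +2.96259, +2.35898 or +2.01404. This requires changing the 2.3 text, the 2.3 boundary table, the 8.1 rule and the trigger together.

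With either option, bring the |Z_i| sentence in SAP 2.2 into line with the one-sided test.

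**Protocol, separately.** In section 7, Sample Size Justification, restate H0 so that benefit lies outside it, and state the same sidedness in both documents. If the one-sided 0.025 test is kept, revise H0 and H1, the two-sided wording and the 0.05 there, and the overall 0.05 and upper/lower boundary columns under Planned Interim Analyses.

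**Cost.** The sign correction is one formula edit, with no effect on patients, data, sample size, boundary magnitudes or count limits. The protocol alignment is a text amendment.
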